Population:	150 randomized participants from recruitment sites in the United States, including both male and female patients of an age ≥ 18 years, diagnosed with systemic scleroderma (SSc) as defined by the 2013 American College of Rheumatology (ACR)/European League Against Rheumatism (EULAR) classification criteria, who demonstrate evidence of active restrictive lung disease by pulmonary function testing, symptomatic dyspnea and any evidence of ground glass opacification (GGO) on baseline thoracic HRCT, and who meet the study definition of being either treatment naïve or recently started on treatment (≤ 6 mo of prior treatment with a potentially disease-modifying therapy) and all other inclusion & exclusion criteria as detailed below.

[figure not shown]
Phase:	Phase II
Number of Sites enrolling participants:	Between 15 to 25 participating clinical sites Please see Section 1, Key Roles, for a current list of participating sites
Description of Study Agents:	
1. Mycophenolate Mofetil (MMF) Manufactured by: Teva Pharmaceuticals, Inc (Generic) Oral Route 250 mg capsules Target Dose: 1500 mg twice daily as tolerated with a 4-step titration at monthly intervals
 
 500 mg (two capsules) twice daily (BID) for 4 weeks 1000 mg (four capsules) BID for 4 weeks 1250 mg (five capsules) BID for 4 weeks 1500 mg (six capsules) BID for remainder of study as tolerated. 
2. Pirfenidone (PFD), same as Esbriet® Manufactured by: Genentech, Inc. Oral Route 267 mg capsules. Target Dose: 801 mg three times daily as tolerated with a 3-step titration at 2 week intervals:
 
 267 mg (one capsule) three times daily (TID) for 2 weeks 534 mg (two capsules) TID for 2 weeks 801 mg (three capsules) TID for remainder of study as tolerated. 
3. Placebo (Plac), matching to the PFD capsules Manufactured by: Genentech, Inc. Oral Route 267 mg capsules. Target Dose: 801 mg three times daily as tolerated with a 3-step titration at 2 week intervals:
 
 267 mg (one capsule) three times daily (TID) for 2 weeks 534 mg (two capsules) TID for 2 weeks 801 mg (three capsules) TID for remainder of study as tolerated.

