4 STUDY DESIGN AND ENDPOINTS

4.1 DESCRIPTION OF THE STUDY DESIGN

The SLS III study is designed as a Phase II multi-center, double-blind, parallel group, randomized and placebo-controlled clinical trial addressing the treatment of patients with active and symptomatic SSc-ILD. Enrollment will occur at 15 to 20 participating academic clinical centers within the United States. 150 patients who are either treatment-naïve or only recently started on treatment (≤ 6 mo of prior treatment with a potentially disease-modifying therapy) will be randomized in a 1:1 assignment to receive either oral MMF and Plac (acting as a control arm) or a combination of oral MMF and oral PFD (acting as an experimental arm), with both regimens administered for 18 months. The target dose for MMF will be 1,500 mg twice daily as tolerated, starting with 500 mg twice daily and proceeding with a 4-step titration at monthly intervals until a maximal tolerated dose or the target dose is achieved for each patient. The target dose for PFD will be 801 mg three times daily as tolerated, starting with 267 mg three-times daily and proceeding with a 3-step titration at 2 week intervals until a maximal tolerated dose or the target dose is achieved for each patient. The length of therapy, 18 months, was established based on prior studies with immunosuppressive therapy alone, which demonstrated that 18 months represents the time required to achieve a peak treatment response. The primary outcomes will include physiologic measures of lung function, HRCT imaging measures of lung inflammatory and fibrotic changes, dyspnea, assessments of skin inflammation and thickening, and patient reported measures of symptoms and quality of life. Tolerability and toxicity of the two treatments will also be assessed.

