- Hold study drug until there is a stabilization of the hematologic abnormality at a value above the toxicity threshold levels indicated above. In addition, if other causes of noted reductions are identified (e.g., gastrointestinal bleeding), they should be treated and stabilized before restarting on study drug.
- Once threshold levels are exceeded (an indication of recovery), MMF will be reintroduced at a daily dose of 1000 mg (500 mg twice daily doses) and increased by 500 mg (one 250 mg capsule for each of the twice daily doses) every two weeks. At the discretion of the clinical site investigator, after taking into account whether the study drug was likely or probably related to the adverse event, the final maintenance dose may be either the last regular dose of MMF taken by the patient or one capsule per-dose less (500 mg/day less).
- In the event of repeat toxicity, the same cycle should be repeated except with the intention of achieving a maintenance dose equal to 1000 mg/day less for MMF.

c) Documentation of gastrointestinal ulcer, bleeding or abdominal emergency.

Dose Management: Management as follows:

- Hold study drug until there is a clinically stable resolution of the problem. In addition, if other causes of noted conditions are identified (e.g., polyps, diverticulitis, untreated peptic ulcer disease), they should be treated and stabilized before restarting on study drug.
- Once a stable recovery occurs, as judged by the clinical site investigator, MMF will be reintroduced at a daily dose of 1000 mg (500 mg twice daily doses) and increased by 500 mg (one 250 mg capsule for each of the twice daily doses) every two weeks. At the discretion of the clinical site investigator, after taking into account whether the study drug was likely or probably related to the adverse event, the final maintenance dose may be either the last regular dose of MMF taken by the patient or one capsule per-dose less (500 mg/day less).
- In the event of repeat toxicity, the same cycle should be repeated except with the intention of achieving a maintenance dose equal to 1000 mg/day less for MMF.

d) Pregnancy or initiation of breastfeeding.

Dose Management: Study drug will be permanently discontinued and subject withdrawn from study.

e) Serum creatinine $> 2.0 \text{ mg/dl}$ or estimated GFR to $\leq 40 \text{ ml/min}/1.73 \text{ m}^2$ (corrected) in the absence of other etiology.

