7.1.2 Standard of Care Study Procedures

7.1.2.1 **Complete medical history and physical examination.** A complete medical history and physical exam covering details related to the patient's history of scleroderma, their entire medical history with a review of systems, and their current physical findings will be

performed during the initial screening visit and at 12 months. This will include a review of pertinent medical records provided by the patient and/or their referring physicians.

7.1.2.2 **Focused Interval history and examination.** A review of current symptoms, medications, physical findings and any changes noted by the patient or a physician since a prior visit will be performed at baseline, monthly for the first 6 months and then every 3 months.

7.1.2.3 **Vital signs.** Vital signs will include: pulse, blood pressure, respiratory rate, temperature (°C), weight (kg), and SpO₂ by pulse oximetry will be performed at initial screening, baseline, monthly for the first 6 months and then every 3 months. Height (cm) will only be done at screening.

7.1.2.4 **Toxicity Monitoring with Blood Tests.** A comprehensive set of laboratory results performed on a current blood sample to evaluate any toxicity or adverse events associated with Scleroderma or its treatment with the study drugs. Blood tests will include: comprehensive metabolic panel (to include serum electrolytes, BUN, Cr, glucose, albumin, ALT, AST, alkaline phosphatase, bilirubin, total protein) and a complete blood count with differential (to include WBC, Hgb, hematocrit, platelet count, and cellular differential count including absolute neutrophil count). Monitoring will occur at initial screening, monthly for the first 6 months and then every 3 months.

In the event that a participant has had all required laboratory tests completed within 30 days of the Screening Visit #1, the results may substitute for the official screening laboratory tests.

7.1.2.5 **Pregnancy Testing.** An initial serum pregnancy test at screening and subsequent monitoring with urine pregnancy testing to be performed on all female participants of child-bearing potential at baseline, monthly for the first 6 months and then every 3 months.

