## 6 Study Methods

### 6.1 General Study Design and Plan

This study is designed as a phase II multi-center, double-blind, parallel group, randomized and placebo-controlled clinical trial addressing the treatment of patients with active and symptomatic SSc-ILD. Eligibility for the study was assessed during a 3-month screening period. Eligible participants were randomized in a 1:1 assignment to receive either oral MMF and Plac (acting as a control arm) or a combination of oral MMF and oral PFD (acting as an experimental arm), with both regimens administered for 18 months.

MMF was administered orally twice daily with a 4-step titration at monthly intervals to a target dose of 1500 mg twice daily as tolerated. PFD/PBO was administered orally three times daily with a 3-step titration at 2 week intervals to a target dose of 801 mg three times daily as tolerated. Patients could receive ongoing treatment with a maximum tolerated dose for either drug that was less than the target dose according to rules defined by the protocol. MMF is approved for use as an immunosuppressant in solid organ transplantation (cardiac, hepatic and renal) at doses up to 1.5 g twice daily and for the treatment of Lupus nephritis, an autoimmune manifestation of systemic lupus erythematosus, in the dose range of 1 to 3 g daily. PFD is currently approved for the treatment of IPF at a recommended dose of 801 mg (3 capsules of 267 mg each) 3 times daily. They were administered in this study at doses that fall within these FDA-defined dosing ranges but as experimental therapy for SSc-ILD.

A participant was considered to have completed the study if he or she completed all phases of the study including the last visit, or the last scheduled procedure, regardless of the dose of either study drug. Participants were followed in the study even if study drug was prematurely discontinued unless they had withdrawn their consent to do so. End of study was constituted by completion of the entire potential 18 months in all randomized participants.

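### The MMF restart is fixed at 1000 mg/day but the reduced maintenance targets have no floor, so at low last regular doses the restart can exceed the target, and after repeat toxicity the target can be zero

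*Protocol*

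**What the plan says.** Protocol 6.1.5.1 gives the same restart cycle in three items: b (bone marrow suppression), c (gastrointestinal ulcer, bleeding or abdominal emergency) and h (other events judged related to MMF). After recovery, "MMF will be reintroduced at a daily dose of 1000 mg (500 mg twice daily doses") and then "increased by 500 mg (one 250 mg capsule for each of the twice daily doses) every two weeks". The final maintenance dose, at the site investigator's discretion, may be "either the last regular dose of MMF taken by the patient or one capsule per-dose less (500 mg/day less"). If toxicity recurs, "the same cycle should be repeated except with the intention of achieving a maintenance dose equal to 1000 mg/day less for MMF".

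The restart dose carries no condition on the earlier dose. The repeat-toxicity instruction has no lower limit and no stated reference dose.

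Low doses are part of the plan. The Protocol Summary starts titration at "500 mg (two capsules) twice daily (BID) for 4 weeks", which is 1000 mg/day. Protocol 4.1 titrates "until a maximal tolerated dose or the target dose is achieved for each patient", and SAP 6.1 confirms that "Patients could receive ongoing treatment with a maximum tolerated dose for either drug that was less than the target dose". On toxicity bloods, Protocol 7.1.2.4 says: "Monitoring will occur at initial screening, monthly for the first 6 months and then every 3 months". For anyone starting at the lowest level, the first on-treatment check therefore falls at the end of the 1000 mg/day step.

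**The concern.** A fixed restart combined with a target defined by subtraction works only if the last regular dose is high enough. At the bottom of the dose range, one item can tell a site to restart at a dose above the one it tells the site to aim for, or to aim for nothing at all.

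The first stake is safety. After marrow suppression or gastrointestinal bleeding, a site that follows the text could restart a participant above the maintenance dose the same item sets. It would also have no instruction for getting down to that dose, because the only steps described go up.

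The second is conduct and data. A zero target looks like stopping MMF. Under 5.3.3 and 6.1.5, stopping MMF also stops the blinded PFD/placebo and leaves only the 12- and 18-month outcome visits, so quarterly FVC-% values used in the primary model would be lost. Nothing says that a zero target triggers this. SAP 6.4.3.5 also measures adherence against the number of pills the protocol prescribes, and that number is unclear where the instructions conflict.

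**Working it through.** **Inputs**
- Restart R = 2 × 500 = 1000 mg/day (6.1.5.1 b, c, h).
- Step = 2 × 250 = 500 mg/day every two weeks (same items).
- Scheduled daily doses (6.1.4.1): 2 × 500, 2 × 1000, 2 × 1250, 2 × 1500 = 1000, 2000, 2500, 3000 mg. The plan's own restart and step figures are reproduced.
- 1500 mg/day is not a scheduled level. It is reached by the first reduction from 2000 (2000 − 500) or during re-titration (1000 + 500).

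**Formulas**, with D the last regular dose in mg/day:
- First-event target: D, or D − 500 at the investigator's option.
- Repeat-toxicity target, reading A: D − 1000, counted from the dose before the first toxicity.
- Repeat-toxicity target, reading B: M − 1000, where M is the maintenance dose in force at the repeat event (D or D − 500).

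Both readings are needed because the text does not choose between them.

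| D | Restart | First-event target | Repeat target, A | Repeat target, B (M = D / M = D − 500) |
|---|---|---|---|---|
| 1000 | 1000 | 1000 or 500 | 0 | 0 / −500 |
| 1500 | 1000 | 1500 or 1000 | 500 | 500 / 0 |
| 2000 | 1000 | 2000 or 1500 | 1000 | 1000 / 500 |
| 2500 | 1000 | 2500 or 2000 | 1500 | 1500 / 1000 |
| 3000 | 1000 | 3000 or 2500 | 2000 | 2000 / 1500 |

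**Reading the table**
- D = 1000, first event: returning to 1000 is consistent with the restart. The optional reduction to 500 is not, since 1000 > 500.
- D = 1000, repeat event: the target is 0, or arithmetically negative under B if the first reduction was taken.
- D = 1500, first event: no conflict (1000 does not exceed 1000 or 1500). Repeat event: the target is 500 (or 0 under B after a reduction), below the restart.
- D = 2000, first event: no conflict. Repeat event: the target equals the restart under A. Under B after a reduction it is 500, below the restart.
- D = 2500 or 3000: the restart never exceeds the target under either reading.

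**The case against.** The best defence has four parts.

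**The first reduction is optional.** This stands. After a first event the investigator may return the participant to the last regular dose at every dose level. A reader might infer that restarting a 1000 mg/day participant at 1000 mg/day contradicts the rule. The documents do not support that, because the text permits rechallenge at the earlier dose after recovery. At a first event the conflict exists only at 1000 mg/day, and only if the reduction is chosen.

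**Investigators have discretion.** Protocol 6.1.5 lets a site depart from the criteria on safety grounds, with reasons documented and the Executive Committee notified within 3 days. That covers situations outside the listed parameters, and these toxicities are listed. It can be argued that an impossible target is itself outside them, but the section aims at near-uniform handling across centres, which case-by-case departures would not give. Item h also offers a restart at half the earlier dose, but only for less severe events under h, not under b or c.

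**The consequence of stopping MMF is already stated.** This is partly right. Sections 5.3.3 and 6.1.5 say what follows MMF discontinuation, and item i of 6.1.5.1 covers toxicity or intolerance lasting 60 days or more. None says that a computed target of zero is discontinuation.

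**The cases may be few.** The documents give no frequency. A zero or sub-restart repeat target needs two toxicity cycles at a low regular dose, and participants continuing pre-study MMF may begin above the first step. This limits the likely number affected but does not resolve the text.

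**Conclusion.** The instructions contradict each other at the low end of the permitted dose range and are wrong as written. The conflict covers 1000 mg/day (the optional first reduction and the repeat target) and 1500 mg/day (the repeat target only). It also covers 2000 mg/day if the repeat subtraction runs from an already reduced dose.

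A reader might infer a clean rule that the conflict arises below 2000 mg/day. The documents do not support that threshold, because it depends on a reference dose they never state. Nor does the text require a reduction after a first event, so it cannot be said that sites must then restart above the dose the rule sets.

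The conclusion assumes that the last regular dose means the daily dose in force before the hold, including a titration step. The number of participants affected is unknown. No sample size, power or type I error figure depends on this point.

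**What to change.** Reconcile the restart, step-up and reduced-maintenance instructions in 6.1.5.1 b, c and h so that the restart cannot exceed the maintenance target at any permitted last regular dose. State the dose from which 1000 mg/day is subtracted after repeat toxicity. State whether a target of zero is MMF discontinuation under 5.3.3 and 6.1.5. Which instruction changes, and to what doses, is for the sponsor's medical lead; none is proposed here.

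The cost is a change of wording in three parallel items, with a cross-reference, and no added procedures. SAP section 14 reports that enrollment stopped before the planned sample size. If treatment is already complete, the useful step is to document how sites applied the rule for participants held and restarted at these doses, including how their prescribed pill counts were set for the adherence calculation.

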Mahler BDI/TDI			X				X				X			X			X			X			X	
SGRQ			X				X				X			X			X			X			X	
SHAQ, PROMIS-29, UCLA SCTC GIT, CRISS, LCQ, Global Assessments	UCLA SCTC GIT		X (except CRISS)								X							X						X
LABS:																								
- CBC, diff, plat	X				X		X	X	X	X	X			X			X			X			X	
- Metabolic/liver	X				X		X	X	X	X	X			X			X			X			X	
- Serum Preg ⁺	X																							
- Urine Preg ⁺			X		X	X	X	X	X	X	X			X			X			X			X	
HRCT		X																						X
Spiro/DLCO	X		X [‡]				X		X	X	X	X			X			X			X			X
Biorepository			X															X						X

[†]Screen and Baseline FVC value must be within an absolute difference in percent-predicted of 10% - may repeat within 7 days if not and proceed to enroll if criteria met

^{*}For women of childbearing potential, initial serum pregnancy testing will be carried out with subsequent urine testing at each visit using test kits provided by the study.

*Exit visit will also be carried out within 30 days (±10d) of early termination/withdrawal from the protocol. All subjects who terminate/withdraw early will be encouraged to return for the outcome assessments as detailed above for the 12 month (V15) and 18 month (V21) visits.

**Refer to Protocol Section 17.0 (EMERGENCY DISASTER/ PANDEMIC MANAGEMENT PLAN) for allowed adjustments in the event of a disaster/pandemic that disrupts patient or institutional access.

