5.3 DISCONTINUING DRUG TREATMENT OR COMPLETE WITHDRAWAL FROM THE STUDY

Patients participating in this study may discontinue active drug treatment but continue with follow-up. They may also completely withdraw from the study (i.e. drop out; end their participation entirely).

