5.3.1 Reasons for Discontinuing Drug Treatment or Withdrawing from Study

Patients participating in this study may discontinue active drug treatment or completely withdraw from the study (or their participation terminated) for the following anticipated reasons.

- 5.3.1.1 Ongoing participation in this research study is voluntary and patients may discontinue active drug treatment or completely withdraw from the study at any time without an identified cause or the need for explanation.
- 5.3.1.2 Patients may also discontinue or be removed from active drug treatment due to adverse events (AEs), laboratory abnormality, or other medical condition or situation such that continued use of one or both of the study drugs is not considered to be in their best interest.
- 5.3.1.3 Patients who become pregnant and/or start breast feeding; which are absolute contraindications to continued therapy, will be required to stop active drug therapy.
- 5.3.1.4 Patients who meet the pre-defined criteria for a “Treatment Failure” (see Section 5.3.2) will be withdrawn from the active drug treatment .

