5.3.3 Handling of Premature Participant Withdrawals

Should a participant prematurely discontinue all active drug treatment for any reason, he/she will be asked to return for key outcome determinations at 12 and 18 months. Their clinical management during the intervals between these visits will be at the discretion of the patient and their treating physician. At the 12 and 18 month visits, any medication prescribed by their treating physician since discontinuing study drug treatment will be recorded in addition to other required assessments for the 12 and 18-month visits. The participant will also be asked to participate in an exit visit, either by phone or in person, to document the reason for withdrawal and the status of the participant at the time of the withdrawal. Should the participant die, the cause of death will be determined and recorded if possible. This additional data will be utilized in the statistical analysis of the primary and secondary study outcomes as defined by the statistical plan.

If only PFD/Plac is prematurely discontinued, and the participant continues to take MMF according to the protocol, then they will continue their participation in all study visits according to the normal study protocol.

If MMF is prematurely discontinued, the participant must stop the PFD/Plac study medication as well and will be asked to return for key outcome determinations at 12 and 18 months. Their clinical management during the intervals between these visits will be at the discretion of the patient and their treating physician. At the 12 and 18 month visits, any medication prescribed by their treating physician since discontinuing study drug treatment will be recorded in addition to other required assessments for the 12 and 18-month visits.

Participants who completely withdraw from the study (drop out; end their participation entirely) will be asked to participate in an exit visit, either by phone or in person, to document the reason for withdrawal and the status of the participant at the time of the withdrawal. Should the participant die, the cause of death will be determined and recorded if possible.

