6.1.5 Pre-specified Dose Adjustment & Modifications

The toxicity profiles for MMF and PFD are well established as outlined in Section 2.3 and drug discontinuation and/or dose modification should be managed in a manner consistent with the following criteria in order to provide a nearly uniform response to pre-defined toxicity at all centers. However, in clinical situations that fall outside of these parameters and if warranted based on good clinical practice, a site investigator may independently modify drug dosing as needed to assure patient safety. If such a change is required, the reasons for the deviation are to be documented and the Executive Committee notified within 3 days. Medications that are contraindicated while on treatment with the study drugs are detailed separately in Section 7.5.

In the event that one study drug is permanently discontinued due to tolerability, adverse event or other medical consideration, then continued use of the remaining study drug will be according to the following pre-specified management:

- If only PFD/Plac is permanently discontinued, the participant may continue to take MMF according to the protocol and continue their participation in all study visits according to the normal protocol-defined schedule of events.
- If MMF is prematurely discontinued, the participant must stop the PFD/Plac study medication as well and will be asked to return for key outcome determinations at 12 and 18 months as detailed in Section 5.3.3 (Handling of Premature Participant Withdrawals).

6.1.5.1 Pre-specified dose adjustments for MMF.

The following abnormalities and laboratory test monitoring results require study drug adjustment, either temporary (until normalization) or permanent, as indicated by the nature of the event, its severity and/or course of resolution upon discontinuation of therapy.

- a) Allergic reaction associated with the administration of MMF.

Dose Management: Study drug will be stopped and subject withdrawn from study.

b) Evidence of clinically significant Bone Marrow Suppression including any one or more of the following

- WBC $<2.5 \times 10^3/\mu\text{l}$
- Absolute neutrophil count $<1.0 \times 10^3/\mu\text{l}$
- Platelet count $<100.0 \times 10^3/\mu\text{l}$
- Hemoglobin $< 10.0 \text{ gm/dl}$ or a drop in hemoglobin to $< 9.0 \text{ gm/dl}$ if the baseline hemoglobin was $< 11.0 \text{ gm/dl}$

Dose Management: Management as follows:

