- Liver function tests should be performed at 7-14 day intervals to monitor as needed based on resulting laboratory and clinical findings.
- Choose one of the following two managments based on the results of repeat liver function testing:
 - iii. If liver function tests worsen (but still do not exceed 5 x ULN) on repeat testing in 7-14 days despite addressing any confounding medications or causes, then the study drug should be held until liver function tests have decreased to ≤ 2 times normal. PFD/Plac should then be re-started at one capsule three times daily, re-titrated using the original study titration protocol (see Section 6.1.4.3) and increased up to the full dosage as tolerated.
 - iv. If liver function tests are stable or show improvement (or continued improvement) on repeat testing in 7-14 days, then the study drug may be handled using one of two options at the discretion of the clinical site investigator:
 - continue at the current dosage without interruption and continue to monitor at 7-14 day intervals.
 - reduce the PFD/Plac dose by 1 capsule for each of the three times daily doses and continue to monitor at 7-14 day intervals.

c) For liver enzyme elevations in a patient who exhibits >3 but $\leq 5 \times$ ULN for ALT and/or AST that is accompanied by clinical symptoms or hyperbilirubinemia after starting PFD/Plac therapy.

Dose Management: Study drug will be permanently discontinued and subject withdrawn from study.

d) For liver enzyme elevations in a patient who exhibits $>5 \times$ ULN for ALT and/or AST after starting PFD/Plac therapy.

Dose Management: Study drug will be permanently discontinued and subject withdrawn from study.

e) For gastrointestinal symptoms that are of sufficient clinical importance to warrant drug dose adjustment (typically involving nausea, diarrhea, vomiting, and dyspepsia), the patient should take the following steps, if not already in place and clinically indicated, prior to considering dose management:

- Take the study medication with food.
- Spread the dose throughout the meal rather than taking all capsules at once.
- Add appropriate pharmacologic therapy to control acid and dysmotility.

Dose Management:

- Reduce PFD/Plac dose by 1 capsule for each of the three times daily doses and if symptoms improve/resolve, can increase back to the original dosing after 2 weeks as tolerated. If the higher dose is still not tolerated, then 1 capsule less for each of the three times daily doses can be continued.

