7.2.4 Final Phone Follow-up Visit / Early Termination Final Phone Visit

Month 19 (Visit #22) or within 30 days of completely withdrawing from study

(Visit window ± 10 d)

- a) Focused interval history
- b) Assessment of adverse events
- c) Review of medications and alternative treatments (if premature termination visit)
- d) Reasons for leaving study (if premature termination visit)

7.2.5 Follow-up for Participants who Prematurely Discontinue Study Drug Treatment or who Completely Withdraw from the Study

Should a participant prematurely discontinue all study drugs he/she will be asked to return for the key outcome determinations at 12 and 18 months, as detailed above. In addition, at that time, any medication prescribed by their treating physician since discontinuing study drugs will be recorded.

The participant will also be asked to participate in an exit visit as detailed in 7.2.4 above. Should the participant die, the cause of death will be determined and recorded if possible.

In the event that one study drug is permanently discontinued due to tolerability, adverse event or other medical consideration, then continued use of the remaining study drug will be according to the following pre-specified management:

- If only PFD/Plac is permanently discontinued, the participant may continue to take MMF according to the protocol and continue their participation in all study visits according to the normal protocol-defined schedule of events.
- If MMF is prematurely discontinued, the participant must stop the PFD/Plac study medication as well and will be asked to return for key outcome determinations at 12 and 18 months as detailed in Section 5.3.3 (Handling of Premature Participant Withdrawals)

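### Protocol 6.1.5.2 c and d withdraw a participant from the study after a liver-triggered pirfenidone/placebo stop, whereas 5.3.3 keeps that participant in follow-up (minor)

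*Protocol*

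**What the plan says.** Rule c of Protocol 6.1.5.2 covers ALT or AST above 3 and up to 5 times the upper limit of normal (ULN) with symptoms or hyperbilirubinemia. Rule d covers any value above 5 times ULN. Both give the same order: "Study drug will be permanently discontinued and subject withdrawn from study".

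Protocol 5.3 separates stopping drug with continued follow-up from leaving altogether. Of the second it says: "They may also completely withdraw from the study (i.e. drop out; end their participation entirely". For people who leave altogether, 5.3.3 provides only a closing contact: "Participants who completely withdraw from the study (drop out; end their participation entirely) will be asked to participate in an exit visit".

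For people who stop drug, the follow-up rules are these:

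- **Protocol 5.3.3.** If only PFD/Plac stops and MMF goes on, the participant continues with every visit. This is written as a directive. If all drug stops, or MMF stops (which forces PFD/Plac to stop too), the participant is asked back at months 12 and 18.
- **Protocol 6.1.5, opening text.** It applies "In the event that one study drug is permanently discontinued due to tolerability, adverse event or other medical consideration", and allows MMF and all visits to continue after a PFD/Plac-only stop.
- **Protocol 7.2.5.** "If only PFD/Plac is permanently discontinued, the participant may continue to take MMF according to the protocol", again with all visits.
- **SAP 6.1.** "Participants were followed in the study even if study drug was prematurely discontinued unless they had withdrawn their consent to do so".

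MMF rules a, d, e and g in 6.1.5.1 also order withdrawal from the study when MMF is stopped.

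**The concern.** A site that follows rule c or d to the letter ends study MMF and FVC-% measurement for a participant whom 5.3.3 keeps in the trial. The quarterly FVC-% series is the primary endpoint, so each such case loses primary outcome data for no analytic reason. The scheduled visits and blood tests after the liver event would also end, although Protocol 8.3 still requires adverse events to be followed until resolved.

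Protocol 2.3.1.2.3 reports that ALT/AST elevations were more frequent on pirfenidone than on placebo in the IPF trials. Any loss would therefore tend to fall in the pirfenidone arm. A participant stopped before month 3 who never returned would also drop out of the modified intention-to-treat set, because SAP 8.2.1 requires a post-baseline efficacy assessment.

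**Working it through.** The plan gives no figure on this point to reproduce. The check compares the texts and then sizes the affected group.

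**Step 1. The texts side by side**

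| Situation | 6.1.5 rules | Follow-up rules |
|---|---|---|
| PFD/Plac stopped under c or d, MMF could continue | Withdrawn from the study | 5.3.3: all visits. 6.1.5 and 7.2.5: MMF and all visits permitted |
| PFD/Plac stopped under c or d, MMF stopped too | Withdrawn from the study | 5.3.3 and 7.2.5: asked back at months 12 and 18 |
| MMF stopped under 6.1.5.1 a, d, e or g | Withdrawn from the study | 5.3.3, 6.1.5 and 7.2.5: asked back at months 12 and 18 |

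The conflict remains whether the term study drug in c and d means PFD/Plac alone or both drugs. Rule i of 6.1.5.2 limits its withdrawal to the treatment phase, so narrower wording was available in the same section. The opening text of 6.1.5 resolves rule i, and no contradiction is claimed there.

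**Step 2. Inputs for the size**

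- SAP 10.1 indexes 51 participants. Assuming an equal split, 51 / 2 = 25.5 per arm.
- Protocol 2.3.1.2.3 (IPF trials): at or above 3 times ULN, 3.7% on pirfenidone and 0.8% on placebo. At or above 10 times ULN, 0.3% and 0.2%.
- Every case at 10 times ULN meets rule d. Not every case at 3 times ULN meets c or d. If IPF rates carry over, the two cut-offs bracket the share affected.

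**Step 3. Expected participants per arm (25.5 × rate)**

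| | Low rate | High rate |
|---|---|---|
| Pirfenidone | 25.5 × 0.003 = 0.08 | 25.5 × 0.037 = 0.94 |
| Placebo | 25.5 × 0.002 = 0.05 | 25.5 × 0.008 = 0.20 |
| Excess on pirfenidone | 25.5 × 0.001 = 0.03 | 25.5 × 0.029 = 0.74 |

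Taking 25 pirfenidone participants at 3.7%:

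- P(none affected) = 0.963^25 = 0.39.
- P(exactly one) = 25 × 0.037 × 0.963^24 = 0.37.
- P(two or more) = 1 − 0.39 − 0.37 = 0.24.

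**Step 4. Expected FVC visits lost at the high rate**

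There are six post-baseline FVC visits, so the arm has 25.5 × 6 = 153. A participant stopped before month 3 loses four visits (months 3, 6, 9 and 15) if he or she returns at months 12 and 18, and six if not.

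- 0.9435 × 4 = 3.8 visits, or 2.5% of 153.
- 0.9435 × 6 = 5.7 visits, or 3.7% of 153.

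These are expected values at an assumed rate, not a maximum. With two participants affected the loss could reach 8 or 12 visits.

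**Step 5. Evidence in this disease**

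Protocol 2.3.1.2.5 reports no clinically relevant liver-test abnormality in the SSc-ILD tolerability study (63 patients, 16 weeks, no placebo arm). Read as 0 of 63, the one-sided 95% upper limit is 1 − 0.05^(1/63) = 4.6%. That is compatible with zero and does not exclude 3.7%.

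**The case against.** The best defense is that the protocol uses the word withdraw loosely. Section 5.3.2 takes treatment failures off drug and invites them back at months 12 and 18, yet speaks of them as having left the study. Section 5.3.3 is titled for withdrawals but opens with people who only stop drug. Section 5.3 ties the end of participation to complete withdrawal, and c and d do not say complete. It can also be argued that a specific rule for serious liver injury may narrow a general permission, and that 6.1.5 and 7.2.5 say only that the participant may continue.

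Part of this stands. The wording may well be shorthand, and 6.1.5 and 7.2.5 alone would be weaker support. But 5.3.3 is a directive, the opening text of 6.1.5 covers a permanent stop of one drug for an adverse event without a liver exception, and rule i shows the narrower phrase in use. A site reading c or d cannot tell which meaning applies.

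Two texts soften the harm. The visit-table footnote says "All subjects who terminate/withdraw early will be encouraged to return for the outcome assessments" at months 12 and 18, though that does not restore the quarterly visits or MMF. SAP 6.1, written in the past tense, suggests that c and d were not in practice applied as an end to follow-up.

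Section 5.3.1.2 adds little to the conflict. It says "Patients may also discontinue or be removed from active drug treatment due to adverse events (AEs), laboratory abnormality" and is silent on leaving the study.

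**Conclusion.** The inconsistency is real and minor. Rules 6.1.5.2 c and d conflict mainly with 5.3.3, and also with 6.1.5, 7.2.5 and SAP 6.1. MMF rules 6.1.5.1 a, d, e and g conflict with the month 12 and 18 rule. The expected number of pirfenidone participants meeting c or d is about 0.1 to 0.9, on the assumptions that IPF rates apply to pirfenidone plus MMF in SSc-ILD and that the 51 participants split equally. Even at the high rate there is a 39% chance that nobody was affected.

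A reader might infer that the rules undermine the missing-at-random assumption in SAP 8.4. The documents do not support that. Treatment is in the primary model, so unequal missingness by arm is not in itself a breach, and nothing shows that visits lost to an ALT/AST trigger depend on unobserved FVC-%. Nor do the documents support a shift in the month-18 effect, a direction of bias, a loss of power, or a claim that participants were actually lost.

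**What to change.** In Protocol 6.1.5.2 c and d, replace the withdrawal clause with: *PFD/Plac stopped permanently; MMF continued or held at the investigator's judgement; follow-up continues under 5.3.3, with all visits if MMF goes on and months 12 and 18 if it also stops.* In 6.1.5.1 a, d, e and g, use: *study drugs stopped permanently; follow-up under 5.3.3.*

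If dosing is complete, the wording change can no longer act. In that case, list from the ALT, AST and bilirubin values and adverse event records already held who met c or d, whether MMF continued, and which FVC visits followed. An empty list, or one with the 5.3.3 visits completed, closes the point.

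The cost is six short wording edits or one listing. No new data or participants are needed, and the decision on MMF after liver injury stays with the investigator.
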